9.4.4.6. Time to a major amputation in the target limb

The log-rank test and Kaplan-Meier methods described in Section 9.4.4.1 will be used for comparing the time to a major amputation between the treatment groups. Similar subgroup analyses will also be performed as described in Section 9.4.4.1.

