3.4.7. RANDOMIZATION AND BLINDING

A randomization schedule with subjects allocated to VM202 (treatment) or placebo (control) in a 2:1 ratio will be used.

The Pharmacist will review the subject's treatment allocation and assigned kit number in IWRS. All documents related to investigational product and treatment allocation will be kept in a secure location with access limited to Pharmacy personnel responsible for preparing the syringes with assigned study treatment.

After study initiation, VM202 and VM202 vehicle (placebo) will be provided to the site's pharmacy. Depending on the assigned study treatment, syringes of VM202 or placebo will be prepared after the clinic notifies the Pharmacy that the subject has arrived in the clinic to undergo study treatment.

This is a double-blind study. The patients, Investigators, study site staff, or Sponsor or any of the Sponsor's representatives or vendors will not know the assigned treatment. Blinding will be achieved by having the study medication (VM202) prepared by the study pharmacist or designee. Reconstituted VM202 is indistinguishable from VM202 vehicle (placebo). The site pharmacist or designee prepares the vials according to the instructions. The site pharmacist or designee and select individuals at the CRO (but excluding blinded study monitors and the blinded clinical trial manager) will be unblinded to the treatment assignments. The subject and study personnel, including core labs, principal investigator, co-investigators, study coordinators, study monitors, data managers, and the clinical trial manager will remain blinded until all data have been entered into the database and the database is locked.

IN CASE OF EMERGENCY ONLY, i.e., SERIOUS ADVERSE EVENT (SAE) AND ONLY WHEN THIS INFORMATION INFLUENCES THE SUBJECT'S

MANAGEMENT AND WHEN KNOWLEDGE OF THE TREATMENT ASSIGNMENT IS ESSENTIAL TO THE WELFARE OF THE PATIENT, the Investigator or designee may request unblinding of that patient. Whenever feasible, the Sponsor (or the Sponsor's representative) should be consulted in advance of breaking the blind for any patient. In any case, the Sponsor (or the Sponsor's representative) must be notified of the unblinding, and the Investigator or designee will document the reason(s) necessary to break the blind for any patient. Complete instructions on this process are detailed in the Study Reference Manual (VMNHU-003 Subject Emergency Unblinding Communication Plan).

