1. INTRODUCTION

This document outlines the statistical methods to be implemented during the analyses of data collected within the scope of Helixmith Co., Ltd. (formerly ViroMed Co., Ltd.) Protocol VMNHU-003/I [A Phase III, Double-Blind, Randomized, Placebo-Controlled, Multicenter Study to Assess the Safety and Efficacy of VM202 to Treat Chronic Nonhealing Foot Ulcers in Diabetic Patients with Concomitant Peripheral Arterial Disease (PAD)]. The purpose of this plan is to provide specific guidelines from which the analysis will proceed. Any deviations from these guidelines will be documented in the clinical study report.

Study enrollment commenced under Protocol VMNHU-003/C. There were 7 subjects enrolled under protocol version C, 5 enrolled under version E, 16 enrolled under version F, and 16 enrolled under version G; no subjects were enrolled under protocol version D, H or I.

Protocol VMNHU-003/E introduced the following changes to exclusion criteria in VMNHU-003/C:

- The study ulcer decreased by 50% or more at baseline from Screening (as assessed by comparison of post-debridement photos taken at Screening and Day 0); previously only ulcers that increased by 50% or more at baseline from Screening were excluded.
- Target ulcer located on an active (hot) Charcot foot; previously any Charcot foot was excluded.
- Body mass index (BMI) > 45 kg/m² at Screening; previously BMI > 35 kg/m² was excluded.
- All steroids except inhaled or ocular steroids; previously only high dose steroids were excluded.

Since these changes to the exclusion criteria were not expected to have a meaningful influence in favor of VM202 on the efficacy and safety parameters, no inferential analyses to account for the protocol version will be conducted. Descriptive summaries of the primary efficacy endpoint and overall adverse event rates will be produced for the subjects enrolled under different versions of the protocol.

Protocol VMNHU-003/F submitted with SAP revision C introduced the following changes to the inclusion criteria:

- the upper age limit for study participants will be raised to 80 years;
- addition of ABI > 1.4 (indicative of non-compressible vessels at the ankle) as a qualifying criterion for documented PAD;
- revision of 1 criterion for documented PAD to: history of lower extremity peripheral artery disease with previous related intervention in a leg.

Protocol VMNHU-003/G introduced the following changes to the exclusion criteria:

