9.4.4.1. Time to complete wound closure of foot ulcer

The log-rank test will be used to compare the distributions of the time to complete wound closure (event) between the treatment groups. Kaplan-Meier estimates of the survival function for each treatment group will be graphically displayed. Kaplan-Meier estimates of quartiles

Helixmith Co., Ltd.

Page 26 of 31

¹ Gail, MH, and Simon, R., Testing for qualitative interactions between treatment effects and patient subsets. Biometrics, 1985;41: 361-372.

(25th, median, and 75th percentiles) with 2-sided 95% confidence interval will be calculated if estimable.

The log-rank test and Kaplan-Meier methods above will be performed for this endpoint for each subgroup identified in Section 7.5 meeting the minimum group size requirement. Differences between the time-to-event distributions of the treatment groups will be compared adjusting for the subgrouping variable using the log-rank test with the subgrouping variable added as a stratification factor in the modeling.

9.4.4.2. Proportion of subjects with a wound closure by 7 months.

The proportion of subjects with wound closure by the 7-month follow-up will be calculated for each treatment group. The 95% confidence intervals of the proportion will be provided based on the binomial distribution and the exact 95% confidence intervals of the proportion difference will also be obtained. Fisher's exact test will be used to compare the proportions between two treatment groups.

The subgroup analyses described in Section 9.4.2 will also be performed for this exploratory endpoint.

9.4.4.3. Percent change in wound volume at 2, 2.5, 3, 4, and 7 months

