The percent change in wound volume at 2, 2.5, 3, 4, and 7 months from baseline will be summarized for each treatment group and compared between the treatment groups using a linear mixed-effects model for repeated measures². The model will include treatment, visit, and treatment-by-visit interaction as the main fixed effects, and baseline wound volume as a covariate using an unstructured variance-covariance matrix. The point estimates for the least-squares mean of the treatment difference (VM202 – Placebo) at each visit and the corresponding 95% confidence interval and p-value will be summarized. Other variance-covariance structures may be substituted if convergence problems arise using corrected Akaike's information criterion (AICC) to pick from among the following structures: compound symmetry (CS), autoregressive ("AR(1)"), variance components (VC), and Toeplitz (TOEP).

The repeated measures analysis above will be performed for this endpoint for each subgroup identified in Section 7.5 meeting the minimum group size requirement. Differences between treatment groups will be compared adjusting for the subgrouping variable using the repeated measures with the subgrouping variable added as a fixed effect in the modeling.

9.4.4.4. Percent change in wound perimeter, area and depth at 2, 2.5, 3, 4, and 7 months

The analyses on the percent change in wound perimeter, area and depth at 2, 2.5, 3, 4, and 7 months from baseline will be based on statistical methods described in Section 9.4.4.3 with the corresponding baseline wound measurement as the covariate.

_

Vonesh, EF and Chinchilli, VM (1996), Linear and Nonlinear Models for the Analysis of Repeated Measurements, New York: Marcel-Dekker.

9.4.4.5. Proportion of subjects with formation of new ulcers on the target foot by 2, 2.5, 3, 4, and 7 months

The proportion of subjects with new ulcers formed by the 2-, 2.5-, 3-, 4-, and 7- month follow-up visits will be calculated for each treatment group. The 95% confidence intervals of the proportion will be provided based on the binomial distribution and the exact 95% confidence intervals of the proportion difference will also be obtained. Fisher's exact test will be used to compare the proportion between the treatment groups at each time point.

The subgroup analyses described in Section 9.4.2 will be performed for these exploratory endpoints.

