9.4.4.7. Time to a minor amputation in the target limb

The log-rank test and Kaplan-Meier methods described in Section 9.4.4.1 will be used for comparing the time to a minor amputation between the treatment groups. Similar subgroup analyses will also be performed as described in Section 9.4.4.1.

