10. INTERIM ANALYSIS

Due to the early stopping of the study, the protocol-specified interim analysis will not be conducted.

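### Target-limb amputations (SAP 9.4.4.6 and 9.4.4.7): if events are few among the 44 subjects, the plan tabulates no by-arm risk with an interval, and its ordinary log-rank p-value is unreliable

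*SAP*

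**What the plan says.** SAP 9.4.4.6 states that the "log-rank test and Kaplan-Meier methods described in Section 9.4.4.1 will be used for comparing the time to a major amputation". SAP 9.4.4.7 states that the "log-rank test and Kaplan-Meier methods described in Section 9.4.4.1 will be used for comparing the time to a minor amputation". Both add subgroup analyses like those for wound closure.

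The section they borrow from, SAP 9.4.4.1, specifies a log-rank test, Kaplan-Meier curves and Kaplan-Meier quartiles: "25th, median, and 75th percentiles) with 2-sided 95% confidence interval will be calculated if estimable". None of these sections names an exact or permutation version, a minimum number of events, or a proportion of subjects amputated per arm.

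For new ulcers on the target foot, SAP 9.4.4.5 takes another route: proportions by visit, exact confidence intervals for the difference, and Fisher's "exact test will be used to compare the proportion between the treatment groups at each time point".

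On sample size, the SAP Introduction reports: "There were 7 subjects enrolled under protocol version C, 5 enrolled under version E, 16 enrolled under version F, and 16 enrolled under version G". SAP Section 10 adds: "Due to the early stopping of the study, the protocol-specified interim analysis will not be conducted". On allocation, Protocol 3.4.7 says: "A randomization schedule with subjects allocated to VM202 (treatment) or placebo (control) in a 2:1 ratio will be used". Neither document gives the realised split of the 44 subjects or an expected number of amputations. SAP 8.4 classes endpoints other than the primary as exploratory, with no multiplicity adjustment.

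**The concern.** Methods suited to wound closure, where many events are expected, are applied unchanged to an event that may be rare. Two things follow if it is rare.

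First, a Kaplan-Meier 25th percentile exists only once about a quarter of an arm has had the event. If that does not happen, the only numerical by-arm summary planned for these endpoints is blank and nothing replaces it. SAP 5.3.2 says that amputations will be noted in the study report. The adverse event tables in SAP 9.5.3 are by system organ class and preferred term, not by target limb or by the SAP's own major and minor categories. A clinically important outcome could therefore be reported with a curve and a p-value, but with no risk per arm and no interval.

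Second, the p-value comes from a large-sample test. With two events it can fall below 0.05 when the exact probability is above 0.10. SAP 9.1 sets two-sided 0.05 for all inferential analyses, so such a result could be quoted as nominally significant.

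**Working it through.** The documents state no event count, power or p-value for amputation, so there is no figure of the plan's to reproduce.

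**Inputs.** Enrolled: 7 + 5 + 16 + 16 = 44 (SAP Introduction). Allocation 2:1 (Protocol 3.4.7); the nearest split is 29:15, which is an assumption, so neighbouring splits are shown. Two-sided 0.05 (SAP 9.1). The amputation risk is assumed and varied. The log-rank test is taken as the usual chi-square version, because no exact version is named. Calculations assume no tied events and no censoring before the last event.

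**Step 1: two events, both on placebo.** With m placebo subjects among N, the expected placebo events are E = m/N + (m−1)/(N−1), and the variance is V = m(N−m)/N² + (m−1)(N−m)/(N−1)². At 29:15:

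- E = 15/44 + 14/43 = 0.3409 + 0.3256 = 0.6665
- V = 435/1936 + 406/1849 = 0.2247 + 0.2196 = 0.4443
- chi-square = (2 − 0.6665)²/0.4443 = 4.00, so p = 0.045 (0.047 if both fall on the same day)
- exact: 15 × 14/(44 × 43) = 210/1892 = 0.111. Both other outcomes are more likely (one in each arm 870/1892, both on VM202 812/1892), so this is also the two-sided Fisher and permutation log-rank p-value.

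| VM202:placebo | log-rank p | exact p |
|---|---|---|
| 27:17 | 0.070 | 0.144 |
| 28:16 | 0.057 | 0.127 |
| 29:15 | 0.045 | 0.111 |
| 30:14 | 0.035 | 0.096 |
| 31:13 | 0.026 | 0.083 |
| 32:12 | 0.018 | 0.070 |
| 200:100 (as planned) | 0.045 | 0.110 |

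The discrepancy comes from the number of events and not from 44 as such: the planned 300 subjects would give the same pair of values. In a median-split subgroup of 22 at 15:7 the pair is 0.031 and 0.091.

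**Step 2: rejection rate with no true effect, by number of events, at 29:15.** All event orderings are enumerated.

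| Events | log-rank | Fisher |
|---|---|---|
| 1 | 0 | 0 |
| 2 | 11.1% | 0 |
| 3 | 3.4% | 3.4% |
| 4 | 1.0% | 1.0% |
| 5 | 3.9% | 3.9% |
| 6 | 1.3% | 1.3% |
| 7 | 7.7% | 3.6% |

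From two to six events every log-rank rejection favours VM202. From three to seven events every Fisher rejection does too.

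**Step 3: unconditional rate.** Weighting the step 2 log-rank rates (continued to higher counts) by Binomial(44, r) gives total two-sided rejection at 29:15 of 0.7% at r = 1%, 2.0% at 2%, 3.05% at 3%, 4.09% at 5% and 3.85% at 10%. The maximum over this range is about 4.1%. The part favouring VM202 is 3.0-4.1% for r = 3-10%, and the part favouring placebo is at most 0.45%. At 28:16 the part favouring VM202 falls to 0.5%, 1.3%, 2.0% and 2.7% at r = 3%, 5%, 7% and 10%.

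**Step 4: can the 25th percentile be estimated?** It needs at least 4 of 15 on placebo (3/15 = 20%, 4/15 = 27%) or 8 of 29 on VM202 (7/29 = 24%, 8/29 = 28%). Binomial tails, with the same risk in both arms:

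| Assumed 7-month risk | Events expected in 44 | Placebo estimable | VM202 estimable | Blank in both arms |
|---|---|---|---|---|
| 5% | 2.2 | 0.5% | <0.1% | 99% |
| 10% | 4.4 | 5.6% | 0.6% | 94% |
| 15% | 6.6 | 17.7% | 5.9% | 77% |
| 25% | 11.0 | 53.9% | 44.3% | 26% |

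These apply to major and to minor amputation separately, each with its own risk.

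**The case against.** **Few events is not documented.** This stands. The only rate in the documents is in Protocol 1.1, where 25% of open wounds are said to progress to gangrene or to need amputation. It has no time frame, includes gangrene, and would mean 11 of 44 if it applied. Low counts are made plausible by 7 months of follow-up, by the split into major and minor, and by the exclusion of gangrene, active infection and amputation foreseen within 3 months (Protocol 3.3.2). They remain an assumption.

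**Blank quartiles are already allowed for.** Also true: a quartile that cannot be estimated is a correct result. But the SAP supplies no substitute. The Kaplan-Meier curve shows cumulative risk by arm, and amputations will be listed and noted, so what is missing is narrower: a by-arm table with intervals.

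**The log-rank test suits the endpoint.** The endpoints are defined as times to amputation, and the log-rank test handles censoring, which a crude proportion does not. This is a good reason to keep the time-to-event definition. It does not justify the chi-square reference distribution at two events.

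**A reader might infer that the test inflates type I error in favour of VM202.** The working does not support that. The two-sided total stays below 5% at 29:15, and an excess appears only if one tail is compared with 2.5%. Even that depends on the split: at 28:16 the tail is below 2.5% for risks of 3-7%. From three to six events at 29:15 the log-rank and Fisher tests reject equally often. Fisher's test shares the lean towards VM202, which largely reflects discreteness under 2:1 allocation.

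**Conclusion.** The point holds as a reporting gap with a fragile p-value, on exploratory endpoints. If the amputation risk is about 10% or less, the quartiles are blank in both arms with probability 94% or more, and no target-limb amputation risk per arm with an interval would be tabulated. At 25% risk that probability is 26%, so blank quartiles are likely but not certain.

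The p-value problem is clearest at exactly two events, both on placebo. The log-rank p-value lies on either side of 0.05 depending on an unstated split (0.035 at 30:14, 0.045 at 29:15, 0.057 at 28:16), while the exact value stays above 0.05 at every split checked. Spurious significance is therefore possible, not assured.

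The conclusions rest on an assumed split near 2:1, assumed low event counts, and the ordinary reading of the log-rank test. They do not show bias in the trial or excess overall error. Priority: consider.

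**What to change.** In SAP 9.4.4.6 and 9.4.4.7:

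- Add n (%) of subjects with a major, and separately with a minor, target-limb amputation by 4 and 7 months in each arm, with exact 95% confidence intervals for each proportion and for the difference, following 9.4.4.5. State how subjects who leave before the visit are counted.
- Keep the time-to-event definition and the Kaplan-Meier curve, but take the p-value from a permutation (exact) log-rank test or from Fisher's exact test.
- Report subgroup results for these two endpoints descriptively, without p-values.

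The cost is SAP wording and a few lines of SAS, with no new data. The downside is small: some nominal p-values become larger. If the data have already been unblinded, report the addition in the study report as a deviation from the plan, for which the SAP Introduction provides.

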9.4.4.7. Time to a minor amputation in the target limb

The log-rank test and Kaplan-Meier methods described in Section 9.4.4.1 will be used for comparing the time to a minor amputation between the treatment groups. Similar subgroup analyses will also be performed as described in Section 9.4.4.1.

9.4.4.8. Change in target limb ABI at 4 and 7 months

Change in ABI at 4 and 7 months will be analyzed in a manner similar to the repeated measurement models described in Section 9.4.4.23 with the baseline ABI values as the covariate.

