3.3.1. INCLUSION CRITERIA

Subjects must satisfy all of the following criteria to be included in the study:

- 1. Male or female, between 18 and 80 years of age;
- 2. Documented history of symptomatic PAD, with one or more of the following criteria satisfied:
 - ABI > 0.40 and \leq 0.90 or > 1.4 (i.e., mild to severe PAD without critical limb ischemia) in target limb;
 - TBI \leq 0.7 in the target limb;
 - Toe pressure of < 55 mm Hg in the target limb;
 - A history of lower extremity PAD with previous related intervention in a leg;

- 3. Documented history of Type I or II diabetes with current treatment control (HbA1c of ≤ 12.0% at Screening) and currently on oral medication, injectable medication and / or insulin;
- 4. No significant changes anticipated in diabetes medication regimen;
- 5. At Screening, subject has one ulcer on the target foot that fulfills all of the following criteria:
 - Present for ≥ 2 weeks and ≤ 1 year
 - Full- thickness and not involving bone, tendon, or capsule (probing to tendon or capsule)
 - No sign of infection or osteomyelitis
 - Ulcer must be $0.5 \text{ cm}^2 15 \text{ cm}^2$ as measured at Screening Visit prior to debridement

If more than one ulcer is present on the foot, the largest ulcer that fulfills inclusion and exclusion criteria will be considered the target (index) ulcer for the study. Subjects will undergo protocol-defined standardized wound care during screening (for two weeks or longer). Subjects will be considered screen failures and will not receive study injections on Day 0 (baseline) if the target ulcer does not meet all entry criteria (see above) as well as being confirmed as non-healing.

- 6. Be capable of understanding and complying with the protocol and signing the informed consent document prior to being subjected to any study related procedures;
- 7. If female of childbearing potential, negative urine pregnancy test at screening and using acceptable method of birth control during the study.

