4.2. Other Efficacy Endpoints

- Time to complete wound closure of foot ulcer
- Proportion of subjects with a target wound closure by 7 months
- Percent change in wound volume at 2 months (Day 60), 2.5 months (Day 74), 3 months (Day 90), 4 months (Day 120), and 7 months (Day 210)
- Percent change in wound perimeter, area and wound depth at 2 months, 2.5 months, 3 months, 4 months, and 7 months
- Proportion of subjects with formation of new ulcers on the target foot by 2 months, 2.5 months, 3 months, 4 months, and 7 months
- Time to major amputation in the target limb
- Time to minor amputation in the target limb
- Change in target limb ABI at 4 months and 7 months
- Change in target limb TBI at 4 months and 7 months
- Change in TcPO₂ at 4 months and 7 months
- Change in the overall quality of life and each domain score (well-being, physical symptoms and daily living, social life) of CWIQ from Day 0 at 4 months and 7 months

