5.4. Derived Variables

Baseline Value

The last non-missing value prior to first dose of study drug. If a subject does not receive any study drug, baseline is the latest recorded measurement on or before the randomization date.

Change from Baseline Value

Change from baseline value is the arithmetic difference between a value of interest and a baseline value: Change from baseline value = (value of interest – baseline value).

Percent Change from Baseline Value

The ratio of the arithmetic difference between a value of interest and the baseline value to the baseline value multiplied by 100: (Change from Baseline / Baseline) \times 100.

Time to Complete Wound Closure

Time to complete wound closure is the time interval (in days) from Day 0 to the date of the first visit date within the allowed visit window where wound closure is so indicated by the investigator. If a subject has not experienced complete wound closure, the subject will be considered censored at the subject's end of study date.

Time to a major amputation in the target limb

Time to a major amputation in the target limb is the time interval (in days) from Day 0 to the earliest date of a reported AE of an amputation of the lower extremity above the ankle of the target limb.

Time to a minor amputation in the target limb

Time to a minor amputation in the target limb is the time interval (in days) from Day 0 to the earliest date of a reported AE of an amputation of a foot or any parts of a foot such as toes on the target limb.

Absolute Differentials

If not provided by the individual study center labs, values for the absolute differentials (i.e., neutrophils, lymphocytes, monocytes, eosinophils, and basophils) will be calculated by multiplying the WBC count by the corresponding percent differential in the total WBC count. Results should be rounded to the nearest hundred for units equivalent to $10^3/\mu L$.

Percent Differentials

If not provided by the individual study center labs, values for the percent differential (i.e., neutrophils, lymphocytes, monocytes, eosinophils, and basophils) will be calculated by dividing the corresponding absolute differential count by the total WBC count. Results should be rounded to the tenth of a percentage point.

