9.4.4. Other Efficacy Endpoints

All the exploratory efficacy analyses will be based on the available data in the ITT population.

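### SAP 9.4.4.8 pools ABI change in limbs above 1.4, which the SAP itself links to non-compressible ankle vessels, with ABI change in all other limbs

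*SAP*

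**What the plan says.** **Entry.** Protocol 3.3.1, criterion 2, requires symptomatic PAD "with one or more of the following criteria satisfied". The ABI option covers values above 0.40 up to 0.90, "or > 1.4 (i.e., mild to severe PAD without critical limb ischemia) in target limb". The other options are TBI, toe pressure, and a history of PAD with a previous intervention. SAP Section 1 records that protocol version F brought the "addition of ABI > 1.4 (indicative of non-compressible vessels at the ankle) as a qualifying criterion for documented PAD".

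**Endpoint.** SAP 4.2 lists "Change in target limb ABI at 4 months and 7 months". SAP 5.4 makes this a signed quantity: "Change from baseline value is the arithmetic difference between a value of interest and a baseline value".

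**Analysis.** SAP 9.4.4.8 says "Change in ABI at 4 and 7 months will be analyzed in a manner similar to the repeated measurement models", with baseline ABI as the covariate. The model described in 9.4.4.3 has treatment, visit, treatment by visit and baseline, and gives one least-squares VM202 minus placebo difference per visit. On the population, SAP 9.4.4 says: "All the exploratory efficacy analyses will be based on the available data in the ITT population".

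I found no rule in either document that excludes, stratifies or separately reports limbs with ABI above 1.4. ABI is not among the planned covariates (SAP 4.5) or the subgroups (SAP 7.5), and the ABI procedure in protocol Appendix 6 does not mention non-compressible vessels. For TBI, SAP 9.4.4.9 does set validity rules: a factor for the measurement method, and omission of subjects assessed by mixed methods.

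**The concern.** The entry criterion treats ABI as disease at both ends of the scale, while the endpoint treats it as a single signed scale. A limb that starts low and a limb that starts above 1.4 stand on opposite sides of the range that does not qualify. Equal signed changes in the two limbs therefore do not carry the same meaning. The SAP adds a reason to doubt readings above 1.4 as a measure of perfusion, because it associates them with vessels that cannot be compressed.

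What is at stake is the reading of one exploratory haemodynamic endpoint. If the treatment changes ABI in limbs where the index works as intended, the pooled difference understates that change. Limbs above 1.4 may also add variation that says little about blood flow.

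**Working it through.** The documents give no SD, effect size or power for ABI, so there is no stated figure to reproduce. The check has a logical part, which rests on the documents, and a numerical part, which rests on assumptions.

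**1. Same signed change, different meaning.** Under inclusion criterion 2 the ranges that qualify are above 0.40 to 0.90, and above 1.4. Values between 0.90 and 1.4 do not qualify on ABI. Three illustrative limbs:

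- 0.70 to 0.90: change +0.20, towards the non-qualifying range.
- 0.70 to 0.50: change −0.20, away from it.
- 1.5 to 1.3: change −0.20, out of the upper qualifying range and into the non-qualifying one.

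The second and third limbs contribute the same value to the model but move in opposite directions relative to the plan's own PAD criterion.

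**2. What the baseline covariate can do.** One baseline ABI term adjusts for the starting level. The model still returns one pooled treatment difference per visit, so it cannot give a separate reading for limbs above 1.4.

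**3. Dilution.** Let f be the share of limbs above 1.4, taken as equal in both arms. Let d be the VM202 minus placebo difference in the other limbs, and g the difference in limbs above 1.4. Then

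pooled difference = (1 − f) × d + f × g.

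With d = +0.05 and g = 0 (both assumed):

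- f = 10%: 0.90 × 0.05 = 0.045
- f = 20%: 0.80 × 0.05 = 0.040
- f = 30%: 0.70 × 0.05 = 0.035

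**4. Noise.** Assume an SD of change of 0.15 in the other limbs, s between 0.30 and 0.40 above 1.4, and equal mean changes. Then

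pooled SD = √[(1 − f) × 0.15² + f × s²].

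| f | pooled SD, s = 0.30 | ratio to 0.15 | pooled SD, s = 0.40 | ratio to 0.15 |
|---|---|---|---|---|
| 10% | √0.02925 = 0.171 | 1.14 | √0.03625 = 0.190 | 1.27 |
| 20% | √0.03600 = 0.190 | 1.26 | √0.05000 = 0.224 | 1.49 |
| 30% | √0.04275 = 0.207 | 1.38 | √0.06375 = 0.252 | 1.68 |

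**5. Both together.** Let r be the ratio of the two SDs and v = (1 − f) + f × r². If g = 0, the efficiency of the all-subject analysis relative to one restricted to the other limbs is (1 − f)² / v divided by (1 − f), that is (1 − f) / v. With r = 0.30 / 0.15 = 2:

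- f = 10%: 0.90 / 1.30 = 0.69
- f = 20%: 0.80 / 1.60 = 0.50
- f = 30%: 0.70 / 1.90 = 0.37

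Under these assumptions, keeping the extra subjects loses precision.

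**6. How many limbs are affected.** SAP Section 1 gives enrolment of 7 + 5 + 16 + 16 = 44. Of these, 16 + 16 = 32 (73%) enrolled under versions F and G, after ABI above 1.4 became a criterion. That is not a count of affected limbs. The PAD criteria are alternatives, so a limb above 1.4 may enter on TBI, toe pressure or history, and most of the 32 may have had lower values.

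**The case against.** The strongest reply is that this is one of many exploratory endpoints, that SAP 8.4 claims no error control for it, and that SAP Section 10 says the study stopped early. With the 44 subjects listed, the ABI model is close to descriptive under either rule. TBI change is already planned in the same population, so a second index exists. All of this stands, and it keeps the point minor.

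Some stronger readings are tempting, and the documents do not support them:

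- *That the endpoint as a whole has no direction.* The difficulty is confined to limbs measured above 1.4. Their number is not given and could be zero.
- *That the plan would score a fall from 1.5 to 1.3 as worsening.* Neither document scores ABI change as improvement or worsening. The plan reports a signed difference, tested two-sided.
- *That readings above 1.4 are falsely high, or that a rise below 1.4 means better flow.* The SAP goes no further than linking such values to non-compressible vessels.
- *That the treatment contrast would have the wrong sign.* The model estimates VM202 minus placebo, so drift common to both arms cancels in expectation. To cancel d = +0.05, the difference between arms in limbs above 1.4 would have to be −(1 − f) × d / f, which is −0.45, −0.20 or −0.12 at f = 10%, 20% or 30%. No passage suggests an effect of that kind.

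**Conclusion.** The point holds as a minor matter of interpretation. Both documents were read in full on ABI, and nothing separates limbs above 1.4, although the entry criterion counts both ends of the scale as PAD and the SAP itself flags the upper end. One pooled difference therefore combines changes that cannot be read in the same direction.

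The supported consequence is dilution and noise in one exploratory contrast. Its size cannot be derived from the documents. The pooled-SD factors of 1.14 to 1.68 depend on assumed SDs and on assumed shares of 10% to 30%, and the dilution from 0.05 to between 0.045 and 0.035 also assumes no treatment difference above 1.4. A systematic reversal of sign is not shown. The primary endpoint, its alpha and its power are not touched.

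**What to change.** Amend SAP 9.4.4.8, before unblinding if that is still possible and otherwise labelled post hoc:

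1. Fit the main ABI-change model in ITT subjects with available data whose measured baseline ABI is 1.4 or less, whichever PAD criterion they entered on. Use baseline as defined in SAP 5.4 (last value before first dose). The screening value that supported entry may differ, since protocol 4.2.8 measures ABI at both Screening and Day 0.
2. Summarise or list subjects with baseline ABI above 1.4 separately by arm, state how many there are, and refer to the TBI analysis in 9.4.4.9 for them. That analysis omits subjects assessed by mixed methods, so it may not cover every such limb.
3. Keep the all-subject model as supportive.
4. Do not drop follow-up values above 1.4 from the main model. That would select on a post-randomisation value of the outcome itself and could remove different subjects in the two arms. Use such a rule at most as a sensitivity analysis.

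The same sentence in 9.4.4.8 cites a Section 9.4.4.23, which the SAP does not contain. The repeated-measures model is in 9.4.4.3, and the reference can be corrected in the same edit.

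The cost is a sentence or two and somewhat fewer subjects in one exploratory analysis. If limbs above 1.4 in fact behaved like the others, the restriction would give up their share of the sample for no gain. The supportive all-subject model covers that case.
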